2.4 Statistical Methods

2.4.1 Demographic and Baseline Characteristics

Continuous data will be summarized using the number of subjects with data available, mean, SD, median, minimum and maximum for each treatment group. Categorical and ordinal data will be summarized using number and percentage of subjects in each treatment group.

Parameters will be summarized for the Principal FAS, PPS, and SS and the Supplementary FAS and SS. The respective NHS populations will also be presented, where applicable.

Parameters will be summarized for a subset of characteristics for the Principal RFAS using the first record after restart.

Parameters described in [Section 2.1.1](#) will be summarized by treatment group and overall using descriptive statistics.

Medical and surgical history will be summarized by SOC and PT sorted by decreasing frequency of SOC and by decreasing frequency of PT within SOC in the MOVE analysis populations. P-values for demographic and baseline characteristics will not be calculated.

No specific description of the safety parameters will be provided at baseline. If relevant, the baseline values will be described along with each safety analysis.

2.4.2 Prior or New Onset Medication

The prior and new onset medications will be summarized based on the enrolled populations as follows:

- Prior medications (excluding systemic glucocorticosteroids) in the MOVE study discontinued prior to the first dose of study drug
- Prior medications (excluding corticosteroids) in the MOVE study ongoing at the first dose of study drug

- New onset medications in the MOVE study (excluding corticosteroids)
- Concomitant medications are any treatments received by the subject after first dose of study drug, and include prior ongoing medications and new onset medications received after first dose of study drug

The medications will be summarized according to the WHODrug Global by Anatomic Therapeutic Class (ATC) and preferred term in the MOVE study. The ATC Class 3 name will be presented if available, and if not available the ATC class 2 name will be presented.

Systemic glucocorticosteroids will be summarized analogously. New onset medications (excluding corticosteroids) and new onset corticosteroids will be summarized by whether the medication was started during chronic treatment or flare-up treatment.

In addition, the NHS only recorded usage of a specific list of medications (Table 6). A summary table presenting the new onset medications in both the MOVE and NHS studies will be presented. In that particular table, only medications that are listed in Table 6 will be included.

Table 6. NHS List of Medications

Prednisone	Montelukast	Narcotics
Other oral steroids	Cromolyn	Calcium
Celecoxib	Etidronate	Vitamin D
Ibuprofen	Pamidronate	Other
Indomethacin	Zoledronate	
Naproxen	Other bisphosphonates	
Other non-steroidal anti-inflammatory (NSAID) medications	Systemic retinoids	
Topical NSAIDs	Thalidomide	
Acetaminophen or similar	Antihistamine	

The tables for prior and new onset medications will be sorted by decreasing frequency of ATC followed by the generic names based on the overall incidence in the MOVE analysis populations. The table summarizing the medications listed in Table 6 will be sorted by decreasing frequency of the drug name listed in the MOVE analysis population.

Corticosteroids used for flare-up treatment is defined as any systemic glucocorticosteroid initiated within 9 days after the start of a flare-up cycle, or initiated within 14 days prior to the flare-up visit or identified on the electronic case report form as a flare-up treated with corticosteroids in the NHS Study.

2.4.3 Study Drug Exposure

The extent of study drug exposure will be assessed and summarized based on the safety populations.

The extent of study drug exposure is defined as: last study drug date – first study drug date + 1. This calculation is regardless of unplanned study drug interruptions.

The duration of chronic dosing, the number of subjects with at least one chronic dose reduction, the number of dose reductions by type (e.g., 5 to 2.5 mg), the number of subjects with interrupted study drug during chronic dosing and the number of subjects discontinuing study drug during chronic dosing will be summarized.

The number of subjects with flare-up dosing, the duration of flare-up dosing overall and by high or low flare-up-based dosing, the number of subjects with at least one flare-up dosing reduction by type, the number of subjects with interrupted study drug during flare-up dosing, the number of subjects discontinuing study drug during flare-up dosing will be summarized.

For chronic and flare-up dosing, a dose reduction is defined as sustained dosing under the expected dose, i.e., underdosing for at least 2 consecutive doses.

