1.4 Context for Version 1.1

This amendment is introduced after the second interim analysis but before the planned third interim analysis (anticipated to be held in mid-May 2020). The futility boundary was crossed at the second interim analysis, signifying that the prespecified Bayesian compound Poisson distribution model with square-root transformation indicated that the trial was unlikely to show sufficient evidence of benefit. The independent data monitoring committee (DMC) informed the sponsor of this outcome on January 15, 2020, and the efficacy assessments were subsequently unblinded to the sponsor.

Based on additional post-hoc analyses presented to the DMC on January 21, 2020, the DMC noted that using the square-root transformation of the data in the primary analysis appears to have moved the statistical conclusion from significant therapeutic benefit to showing futility of the treatment. The DMC also noted that the dilemma created by these highly disparate results precludes a confident conclusion about futility. As such, the DMC recommended that additional analyses be conducted and provided to them for consideration at the next interim analysis.

US FDA instituted a partial clinical hold on dosing of palovarotene due to premature physcal closure (PPC) for subjects <14 years of age on December 4, 2019; as of the finalization of this SAP amendment, dosing has not yet resumed for these subjects. Dosing on all other subjects not subject to US FDA's partial clinical hold was interrupted following the January 21, 2020 DMC meeting while the protocol amendment allowing the continuation of the study after the futility outcome and incorporating the additional analyses requested by the DMC was reviewed by regulatory agencies, IRBs, and investigational sites. These subjects had palovarotene dosing interrupted on or around January 24, 2020. The sponsor allowed dosing to resume as of March 26, 2020, provided each individual site had obtained Ethics Committee approval to do so and the site was able to fulfil regulatory and operational requirements. Subjects were expected to restart dosing over a span of weeks due to these logistical considerations.

Note that Sections 1.3 (Study design), 1.4 (Objectives), 1.5 (Determination of sample size) and 1.6 (Study plan) were unchanged from the SAP V1.0, which was finalized prior to the first

interim analysis. New content began in Section 1.7 (Modifications to the statistical section of the protocol).

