2.1.4 Safety Endpoints

Safety evaluations will include adverse event (AE) and serious AE (SAE) reporting, electrocardiograms, vital signs (temperature, respiratory rate, blood pressure, and heart rate),

physical examination, body weight/BMI, knee and linear height, laboratory parameters (hematology, biochemistry, and urinalysis), urine pregnancy tests for FOCBP, radiographic imaging and whole body computed tomography (WBCT), concomitant medication reporting, and the age-appropriate C-SSRS.

Adverse Event Variables

Adverse Event Observation Periods

- A Pre-treatment AE is an AE with an onset date before the first dose of study drug.
- TEAEs are AEs with (first dose date of study drug) \leq (AE start date) \leq (last dose date of study drug +7 days for all AEs, i.e., non-serious and serious AEs).
 - A chronic TEAE is a TEAE with an onset date during chronic treatment
 - A flare-up TEAE is a TEAE with an onset date during flare-up treatment
- Post-treatment AEs are AEs with a start date $>$ last dose date + 7 days for All AEs (non-serious and serious AEs).

Note that subjects may have multiple independent flare-up treatment cycles, each potentially with associated AEs, within the study.

For the efficacy interim analysis and final analysis, treatment emergence for chronic or flare-up treatment is determined based on the subject's dosing diary. For all other pre-lock analyses, treatment emergence is determined using the subject's planned dosing log if insufficient diary data is available, with the date of the extract of data for the interim analysis used as the end date for TEAE assignment purposes.

Any AE with a missing start date is considered TEAE. For TEAEs that have a partial date where the day is missing, if the month is the same month as a flare-up treatment was given, then the TEAE will be defined as a TEAE associated with flare-up dosing.

All AEs (including SAEs) will be coded using a current or recent version of MedDRA. Adverse event severity will be assessed and reported according to criteria defined in the protocol (mild, moderate, severe). Adverse event causality will also be assessed in terms of relationship to study drug and reported according to criteria described in the protocol (not related, possibly related, probably related, definitely related).

The occurrence of AEs (including SAEs) will be recorded from the time of signed informed consent until the end of the study.

Deaths

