Hearing was assessed via age-specific pure tone audiogram monitoring via baseline and follow-up age-specific hearing evaluation tests. A listing will summarize by-subject results.

Pregnancy and Teratogenicity Assessment

Pregnancy and pregnancy outcomes were monitored throughout the study. A listing will summarize by-subject results.

Bone Safety Assessments

Two events led to a prolonged treatment interruption period. The first interruption occurred following a partial clinical hold issued by the US Food and Drug Administration (FDA) on the 4 December 2019 for subjects under 14 years of age in palovarotene clinical studies due to the identification of the risk of PPC. The second interruption occurred following the outcome of the PVO-1A-301 second interim analysis that crossed the threshold for futility, which resulted in the per-protocol treatment discontinuation of subjects ≥ 14 years of age on 24 January 2020.

Bone safety data will be described for following time periods:

The Original Baseline Period

The original baseline period will be defined by the original baseline through February 2020.

The Interruption (Off-treatment) Period

The baseline for the off-treatment period is the earlier of the first assessment while off-treatment or the assessment within 1 month prior to the last dose of palovarotene. Bone growth assessments during the interruption period included subjects in the off-treatment population, which was defined as subjects < 18 years of age at first study entry who interrupted palovarotene after the clinical hold date and did not re-initiate treatment and who had an off-treatment baseline and post-off-treatment baseline visit.

The end of the interruption period occurred either at the end-of-treatment/end of study visit if the subject discontinued from the study, at the end-of-study visit if they completed the study, at the new baseline if the subject re-initiated palovarotene treatment.

The New Baseline Period

A new baseline was established by the re-initiation of palovarotene dosing following the interruption period. New baseline bone growth assessments includes all subjects who had a new baseline and a post-new baseline visit and received at least one dose of palovarotene after the new baseline visit date. The new baseline visit date was defined as the date of the last visit prior to the re-initiation of palovarotene treatment following the interruption period.

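### For subjects who restarted after the January 2020 stop, the SAP counts about two off-drug months as exposure and as the treatment-emergent period

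*SAP*

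**What the plan says.** **Exposure.** SAP 2.4.3, summarised on the safety populations: "The extent of study drug exposure is defined as: last study drug date – first study drug date + 1". The next sentence adds "This calculation is regardless of unplanned study drug interruptions".

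**AE periods.** Under SAP 2.1.4 a TEAE starts on or after the first dose and no later than "last dose date of study drug +7 days for all AEs". Post-treatment AEs are those starting after that same limit. A chronic or flare-up TEAE is one with onset during the corresponding treatment, judged from the dosing diary at the efficacy interim and final analyses.

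**The stop.** SAP 1.4: "Dosing on all other subjects not subject to US FDA's partial clinical hold was interrupted following the January 21, 2020 DMC meeting". The date follows: "These subjects had palovarotene dosing interrupted on or around January 24, 2020". Then: "The sponsor allowed dosing to resume as of March 26, 2020", conditional on ethics approval and site readiness, with restarts expected to spread over weeks. The under-14s had been held since 4 December 2019, and SAP 1.5 says treatment will not be restarted in children under 14.

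**Where the SAP does address the gap.** SAP 2.4.4 limits the main efficacy analyses to assessments on or before the interruptions, with all-timepoint versions alongside. SAP 2.3 creates an analysis set for restarters. SAP 2.4.5 opens its bone-safety section with "Two events led to a prolonged treatment interruption period" and defines original-baseline, interruption and new-baseline periods. SAP 2.4.8 and 2.4.9 subtract untaken or interrupted days from flare-up and non-flare-up durations.

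**The concern.** A first-to-last-dose convention is harmless for scattered missed doses. This was a single planned stop for every MOVE subject still on drug, and other parts of the SAP treat it as important enough to need its own rules. The exposure definition and the general TEAE window have none.

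Two things are at stake. The stated extent of exposure, which readers use to judge how much safety experience exists, includes a block of time when nobody was dosed. And the label on an off-drug AE depends on what the subject did later: the same event on the same calendar day is treatment-emergent in a restarter and post-treatment in a subject who stopped for good. Assessments continued during the interruption (SAP 1.10.2), and Protocol 7.8 asks for AE review in subjects waiting to restart, so events in this interval would be recorded.

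**Working it through.** The documents give no length for the gap, so there is no stated figure to reproduce.

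**Length of the gap** (dates from SAP 1.4; 2020 is a leap year)
- 24 January to 26 March 2020 = 7 days left in January + 29 in February + 26 in March = 62 days.
- Last dose 23 January and restart 26 March: 24 January to 25 March is drug-free, 8 + 29 + 25 = 62 days.
- Last dose 24 January: 61 days.
- If 'on or around' means within 7 days either side (my assumption), the date difference is 55 to 69 days. Later site restarts lengthen it.

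**Effect on exposure.** The SAP 2.4.3 formula has no term for off-drug days, so a restarter's recorded exposure contains the whole gap. First-to-last-dose spans are not in the documents; those below are assumptions. Share = gap / recorded span.

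| Assumed case | Recorded span (days) | 62-day gap | 90-day gap |
|---|---|---|---|
| 12 months before the stop, then the gap, almost no dosing after | 365 + gap | 62/427 = 14.5% | 90/455 = 19.8% |
| 24 months | 730 | 62/730 = 8.5% | 90/730 = 12.3% |
| 48 months | 1461 | 62/1461 = 4.2% | 90/1461 = 6.2% |

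The first row is the upper end for a Principal Enrolled Population subject with 12 months of dosing before the stop. The second interim analysis was timed for 12 months of follow-up in that population (SAP 3), and its futility result preceded the stop (SAP 1.4).

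**Effect on AE classification** (illustrative subjects). Two subjects each take a last pre-gap dose on 24 January 2020 and have an AE starting on 1 March.
- Subject X never restarts. The limit is 24 January + 7 = 31 January. The AE is later, so it is post-treatment.
- Subject Y restarts on 26 March. The last dose is now after 1 March, so the AE is a TEAE.

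The days on which the two labels differ number 61 - 7 = 54, or 62 - 7 = 55 if the last dose was 23 January.

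**Which column.** SAP 2.4.5 tabulates TEAEs by chronic dosing, flare-up dosing and overall. Subject Y's AE enters the overall column. The diary shows neither kind of dosing on 1 March, which points away from both other columns. SAP 2.4.9, however, assumes subjects are on non-flare-up treatment unless they are receiving flare-up treatment, which points to chronic. No rule settles it.

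**The case against.** The case for leaving the plan alone has several good points.

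- **Net durations already exist.** SAP 2.4.8 and 2.4.9 subtract interrupted days, and SAP 2.4.3 also lists durations of chronic and flare-up dosing and counts of subjects with interruptions. This stands in part. SAP 1.10.3 ties the net durations to compliance, SAP 2.1.7 summarises compliance on the Principal FAS, and SAP 2.4.3 does not say that its own durations are net. The safety-set exposure figure remains gross.
- **The long window is conservative.** It can only add events to palovarotene, and relatedness is assessed separately. This stands, and it is why gap AEs should not simply be dropped from the TEAE tables. It does not excuse the exposure figure, which errs towards more apparent experience.
- **No rate is diluted.** A reader might infer that inflated exposure lowers AE rates. AE percentages in SAP 2.4.5 use subject counts, and no exposure-adjusted rate is planned.
- **Bone safety is not a clean contrast.** A reader might infer that bone safety treats restarters' gap as off-treatment while the AE tables do not. Its interruption period does end at the new baseline for those who re-initiate, but the off-treatment growth population excludes them and the original-baseline period runs through February 2020, well into the gap.
- **Reach may be limited.** SAP 3.3 does not plan to rerun interim-CSR analyses. If that covers the safety tables, only restarts before the third interim data cut are affected. Against this, Protocol 8.5.3 requires safety summaries over Parts A, B and C together.

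**Conclusion.** The point holds for MOVE subjects who restarted. At least about 61 to 62 off-drug days count as exposure. AEs starting in roughly the last 54 to 55 of those days are labelled by whether the subject later restarted, with no clear chronic or flare-up assignment. Subjects who never restarted are unaffected.

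The share of recorded exposure rests on assumed spans: 14.5% at most for a Principal subject dosed 12 months before a 62-day gap, 8.5% at 24 months, 4.2% at 48 months, and more if the gap was longer. The numbers of restarters and of gap AEs are not in the documents, so the amount of reclassification cannot be sized.

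Three stronger readings are not supported:
- That the gap is 17% of exposure (62/365.25). A recorded span of only 12 months including the gap does not fit the timing of the second interim analysis for Principal subjects.
- That a gap AE is definitely neither a chronic nor a flare-up TEAE. The SAP is ambiguous on this.
- That the January stop was programme-wide. SAP 1.4 describes it for MOVE; the under-14 hold was the programme-level action.

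**What to change.** - **Exposure.** In the safety set, report exposure net of interrupted days beside the first-to-last-dose figure, built on the SAP 2.4.8 and 2.4.9 durations. One check is needed: SAP 2.4.9 subtracts the net flare-up duration, so days missed inside a flare-up cycle drop out of SAP 2.4.8 but stay in the non-flare-up figure. If a cycle spans the stop, subtract those days explicitly.
- **AEs.** Keep the existing TEAE tables. Flag AEs starting more than 7 days after the last pre-interruption dose and before restart, and tabulate them separately as off-treatment. Add a TEAE summary excluding them as a sensitivity analysis.
- **Column rule.** State where a flagged AE goes in the chronic and flare-up columns.

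No new data are needed: restart and interruption dates are already required for the restart analysis set, the new bone-safety baseline and SAP 2.4.9. The cost is some SAP wording, a few extra tables and a slightly smaller stated exposure. Removing gap AEs from the main TEAE tables is not recommended, because that would be the less conservative choice.

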2.4.4 Analyses of Efficacy Endpoints

The efficacy endpoints will be analyzed using the Principal FAS. Analyses using the Principal PPS will be performed as noted. Listings will be generated for the Supplementary FAS.

Note that no statistical inference is planned to be included in the descriptive analysis to be conducted before the first formal interim efficacy analysis; the inference described in this section will be conducted for the three interim efficacy analyses.

In order to address the prolonged interruptions in dosing in subjects <14 years old upon US FDA's institution of a partial clinical hold due to premature physéal closure (PPC) on December 4, 2019 and interruptions in dosing for the remaining subjects on January 24, 2020 due to the crossing of the futility boundary at the second interim analysis, analyses of all efficacy endpoints will include assessments collected on or before these interruptions, unless otherwise specified. (Assessments were to continue as planned during the interruptions.) For IA3, analyses in which all timepoints (available at IA3) are included, irrespective of dosing interruption, will also be conducted for the primary analysis (and additional analysis without the square-root transformation) and secondary analyses to aid in the interpretation of the efficacy results.

Note that, due to the prolonged interruption, IA3 provides the best description of efficacy of palovarotene and is determined to be the 'final analysis' for efficacy.

Additional analyses will be performed after database lock in which all WBCTs are included. E.g., an analysis comparing annualized new HO volume with NHS will be performed using GEE – Bayesian analyses are not planned. A separate analysis will also be performed for subjects who re-started palovarotene after the interruptions described above in the Principal RFAS. Baseline will be defined as the first WBCT scan obtained after re-start that was not obtained during a flare-up or within 1 month of the end of a flare-up.

The sponsor also notes that because the futility boundary was crossed at the second interim analysis, all subsequent analyses of efficacy data will be supplied without applying thresholds for success or futility, as these thresholds are no longer relevant.

Analyses of Primary Efficacy Endpoint

Primary Analysis

The primary efficacy endpoint is the annualized change in new HO volume (as assessed by WBCT). The change in new HO volume is calculated by summing the increase in HO volume across all body regions for which new HO has occurred where the increase in HO volume per region is defined as the square-root of the volumetric increase in that region. The square-root transformation is used to reduce the influence of outliers. Transformation of volumetric changes has been used in related contexts. For example, a log transformation has been used to model volumetric increases in the kidneys of subjects with autosomal dominant polycystic kidney disease^{1,2}. The change in new HO volume is modeled using a Bayesian compound Poisson distribution. The Bayesian compound Poisson distribution assumes that the change in new HO volume can be modeled as a compound distribution of the number of body regions with new HO, K , and the new HO volume per region where new HO has occurred, Z . The number of body regions with new HO in subject i for WBCT scan j with duration w_{ij} (the time between scan j and the previous scan) is distributed as

$$K_{ij} \sim \text{Pois}(\lambda_{i,j} * w_{ij} * \theta_{1,t(ij)});$$
$$\log(\lambda_{i,j}) = \log(\lambda_i) + \beta_1 X_{1,i} + \beta_2 X_{2,i,j}$$

The subject-level rate λ_i follows a gamma distribution and accounts for potential correlation in measurements from the same subject; $t(ij)$ is an indicator function equal to 1 if the subject was on treatment at the time of the j th WBCT scan and 0 if the subject was not on treatment. Therefore, the marginal distribution of the number of body regions with new HO follows a negative binomial distribution, which requires much less restrictive assumptions than a Poisson distribution and does not tend to result in an underestimate of the variance.

Letting $\theta_{1,0} = 1$, the variable $\theta_{1,1}$ is the multiplicative effect of palovarotene treatment on the rate of body regions with new HO. Covariates are included in the analysis of the number of body regions with new HO to adjust for potential explained differences in the rate of new HO based on the subject's sex, $X_{1,i}$, and age at time of scan, $X_{2,i,j}$. Age at the time of scan is represented as a factor variable with 0 for <18 years old and 1 for ≥ 18 years old. Covariate effects $\exp(\beta_1)$ and $\exp(\beta_2)$ are multiplicative effects of sex and age on the rate of body regions with new HO.

The new HO volume (square-root of the volumetric increase in that region) in region r , $\sqrt{Z_{ijr}}$, where new HO has occurred for subject i in scan j is assumed to be distributed as:

$$\sqrt{Z_{ijr}}/1000 \sim N\left(\alpha * \alpha_r * \theta_{2,t(ij)}, \frac{\alpha_r^2}{\tau_{t(ij)}}\right).$$

The scale of new HO volume is modeled in the thousands. Letting $\theta_{2,0} = 1$, the variable $\theta_{2,1}$ is the multiplicative effect of palovarotene treatment on the new HO volume conditional on new HO occurring. The α_r are region-specific variables that contribute to the mean of new HO and the variance; the restrictions $\alpha_r = \alpha_{r'}$, where r and r' are a left and right region pair are included, i.e., right chest and left chest, right arm and left arm, right hip and left hip, and right lower leg and left lower leg. The precision variables, τ_0 and τ_1 , introduce flexibility by allowing variability to differ between new HO volume in treated subjects and untreated subjects.

The prior distributions for the variables in the Bayesian compound Poisson distribution are the following:

$$\begin{aligned}\lambda_i &\sim \text{Gamma}(a, \text{scale} = b) \\ \beta_1, \beta_2 &\sim N(0, 2^2) \\ a, b &\sim \text{Gamma}(1, 1) \\ \alpha &\sim N(0, 1) \\ \alpha_r &\sim \text{Unif}(0, 4) \\ \tau_0, \tau_1 &\sim \text{Gamma}(1, 0.01) \\ \theta_{1,1}, \theta_{2,1} &\sim \text{Unif}(0, 2).\end{aligned}$$

All gamma distributions are parameterized as the shape and rate, except as noted for λ_i . The primary efficacy analysis comparing the annualized change in new HO volume between subjects treated with palovarotene and untreated subjects is performed by calculating the ratio of the annual mean change in HO volume in palovarotene treated subjects to untreated subjects using the Principal FAS and assuming missing at random.

In this SAP, new HO is deemed to be present in a body region if the volume of net new HO is greater than zero, i.e., the change in volume of HO in a region between two timepoints is positive. (Volumes of individual lesions are not assessed; the net volume of HO in a body region is reported.). Any regions with amounts of new HO $< 0 \text{ mm}^3$, i.e., reductions in the volume of HO over time (which can happen due to bone remodeling or measurement variability), will be represented as having no new HO and the volumes will be set to zero in the analysis.

Missing timepoints for subjects, i.e., assessments not conducted, assessments conducted but not evaluable for the presence of HO or volume of HO, or assessments for which HO volume for at least 50% of body regions is not evaluable or not available, will not be imputed. Body regions with non-evaluable HO volume at a timepoint will be represented as having no new HO and the volumes will be set to zero in the analysis.

As described in the MOVE and NHS Independent Review Charter, adjudication is by timepoint. When adjudicated, analysis will use the adjudication assessment of volume of new HO. When not adjudicated, the average of the two readers' amounts of HO for each body region will be used, assigning a volume of 0 mm^3 if the reader does not measure due to the qualitative assessment of no new HO.

Using the Bayesian compound Poisson model described above, the efficacy ratio γ is calculated as the treatment effect on the mean number of body regions with new HO, $\theta_{1,1}$, multiplied by the

treatment effect on new HO volume conditional on new HO occurring, $\theta_{2,1}$, expressed as $\gamma = \theta_{1,1} * \theta_{2,1}$. Random samples generated via Gibbs sampling from the posterior distribution of $\theta_{1,1}$ and $\theta_{2,1}$ will be used to compute the posterior probability that $\gamma < 1$ to determine statistical significance.

Additional Analyses

The primary efficacy analysis described above will be repeated without the square-root transformation. As noted by the DMC after the second interim analysis, using the square-root transformation of the data in the primary analysis was impactful in that it appeared to have moved the statistical conclusion from significant therapeutic benefit to showing futility of the treatment.

Furthermore, as is explained later in this section, the square-root transformation together with the more frequent WBCT efficacy assessments in MOVE relative to NHS seem to introduce a bias against palovarotene in the primary analysis.

Also, with its square-root transformation reducing the influence of subjects with unusually large amounts of new HO, the primary analysis is expected to be less powerful relative to the analysis without the square-root transformation if an effect of palovarotene is to reduce the chance of catastrophic HO as is suggested in the results observed thus far in MOVE (and was also observed in post-hoc analyses of flare-up-based imaging endpoints in earlier studies).

For these reasons, while acknowledging that it is post-hoc, the sponsor believes that the Bayesian compound Poisson analysis without the square-root transformation is the more appropriate analysis of the primary endpoint, relative to the Bayesian compound Poisson analysis with the square-root transformation. The Bayesian analysis without square root transformation is referred to as the analysis of primary interest.

When performed without the square-root transformation, the new HO volume in region r , Z_{ijr} , where new HO has occurred for subject i in scan j is assumed to be distributed as:

$$Z_{ijr}/1000 \sim N\left(\alpha * \alpha_r * \theta_{2,t(ij)}, \frac{\alpha_r^2}{\tau_{t(ij)}}\right).$$

The prior distributions for the variables in this Bayesian compound Poisson distribution are the following:

$$\begin{aligned} \lambda_i &\sim \text{Gamma}(a, \text{scale} = b) \\ \beta_1, \beta_2 &\sim N(0, 2^2) \\ a, b &\sim \text{Gamma}(1, 1) \\ \alpha &\sim N(0, 10^2) \\ \alpha_r &\sim \text{Unif}(0, 4) \\ \tau_0, \tau_1 &\sim \text{Gamma}(1, 100) \\ \theta_{1,1}, \theta_{2,1} &\sim \text{Unif}(0, 2). \end{aligned}$$

The Bayesian compound Poisson model will be fitted using the R statistical computing language and environment. The R programs will be run using v3.5.0 or later; packages used, including version number, will be identified in the CSR.

Additional supportive analyses including the weighted mixed linear effect (wMLE) analysis with and without the square-root transformation will also be performed. The wLME analysis without the square-root transformation was previously the primary efficacy analysis, before the Bayesian compound Poisson analysis was added in Amendment 1 of the protocol. This wLME analysis without square-root transformation is referred to as the alternative analysis of primary interest.

A subject-level random effect will be used to account for the correlation among repeated measures on the same subject as subjects may contribute follow-up from both the NHS and the current study. Baseline HO volume divided by age will be the only covariate included in the model, in addition to the factor identifying study of origin. The LME model will be fitted using only a subject's observations associated with the longest follow-up in the NHS and the current study with weights used to account for the different lengths of observed subject follow-up. Missing at random will be assumed for the primary analysis and no imputation of missing data performed.

The wLME analyses will be run using SAS 9.4 or higher. The code will use the following structure:

```
proc mixed data=data;
    class treat usubjid;
    model annrate_newho = treat basetot_bage /s;
    random usubjid;
    lsmeans treat/pdiff=control('0') cl;
    weight fup;
run;
```

In this code, treat is a binary indicator for study (1=MOVE, 0=NHS); usubjid is a unique identifier of subjects (used across all FOP studies); annrate_newho is the annualized rate of new HO; and fup is follow-up in years.

The Bayesian compound Poisson analysis and wLME analysis without square-root transformation and including all assessments on or before December 4, 2019, for subjects <14 years old on the date of their assessment and assessments on or before January 24, 2020, for all other subjects, will be repeated using the Principal PPS after the third interim analysis.

Descriptive statistics summarizing the total HO by study visit, change in HO volume by study visit, and change in HO volume from baseline by study visit will be provided. Tables summarizing annualized new HO will also be produced. Summaries will also be provided by body region. Summaries of new HO coincident with flare-ups and not coincident with flare-ups will also be generated. Summaries of annualized mean New HO, conditional on new HO volume>0 mm³, will be created. HO listings will also be generated.

Missingness, including frequency of WBCT not collected and regions that are not evaluable, will be summarized. Frequency of negative new HO, i.e., apparent reductions in HO overall and by body region (defined below), will also be summarized.

Handling of Reductions in HO

Please note that, as referenced above, the Bayesian compound Poisson models with and without square-root transformation assume non-negative changes in HO volume for each subject for each region, and any apparent reductions in HO volume over time (i.e., negative new HO volumes) are “zeroed out”, i.e., replaced with zero. (All analyses of square-root transformed new HO volumes require non-negative new HO volume in order for the square-root transformation to be applied.) In contrast, because wLME is a regression method, it is less specialized and can accommodate the negative values when applied to non-transformed data.

However, in order to understand the relative contributions to the results of 1) zeroing out the negative changes; 2) square-root transformation of the zeroed out new HO volumes; 3) using a body-region or overall whole body based analysis; 4) using data on intervals between WBCTs, not just the first and last timepoint; 5) Bayesian compound Poisson analysis; we will run five wLME “series”:

1. Raw, untransformed data (i.e., including all negative values)
2. Zero out overall whole-body new HO without square-root transformation
3. Zero out overall whole-body new HO with square-root transformation
4. Zero out by region [by visit] without square-root transformation
5. Zero out by region [by visit] with square-root transformation

For series 2 and 3, the sum of new HO at the last timepoint, i.e., changes from baseline including negatives, is added across body regions. If negative, the sum is replaced with zero. For series 3, the sum is square-root transformed. Then the sum – or square-root of the sum – is divided by time in years, resulting in the annualized new HO.

For series 4 and 5, negative changes in HO volume by region (from previous visit) are replaced with 0. For series 5, the square-root of each change is taken. These numbers are then added across timepoints and body regions and their sums are divided by time in years, resulting in annualized new HO. This method for constructing annualized new HO, with and without square-root transformation, yields wLME analyses that are the closest analogs to the Bayesian compound Poisson analyses.

Note that in applying the square-root transformation to zeroed out new HO for intervals, wLME using series 5 should be subject to the same bias as is attributed to the Bayesian compound Poisson primary analysis illustrated later in this section.

Control of Type I Error

Ninety-nine palovarotene-naïve subjects with the R206H ACVR1 mutation were enrolled into the current trial and are to be followed for 2 years. There were to be three early interim efficacy analyses and one final analysis. Futility was declared at the second interim analysis, but the study continued. The final analysis for Part A will occur when all subjects have completed 2-year follow-up. (Note that, as described, due to the prolonged palovarotene interruption prior to the completion of Part A, IA3 is designated the final analysis.)

The first interim analysis was to take place when approximately 35 MOVE subjects complete 1 year of follow-up with the second and third interim analyses occurring when all subjects in the Principal EP have the opportunity to have complete (i.e., have WBCT data) 12 months and then 18 months of follow-up, respectively. It was assumed that the full NHS dataset will be available at the first interim analysis. The amount of statistical information at each interim analysis can be approximated by the sum of the follow-up in each study divided by the total expected. The total follow-up expected across the NHS and the MOVE Trial is 317.5 years (NHS: 45*1.5 years + 45*2.0 years; MOVE: 80*2.0 years). Assuming eight subjects enroll in the MOVE study per month, the percentage of subject follow-up for each analysis is summarized in Table 7 where values with an asterisk indicate approximate information based on expected accrual rates and total planned accrual in the Principal EP.

Table 7. Observed MOVE Follow-up at Each Planned Analysis

Analysis	Observed MOVE follow-up	Percentage of follow-up available
Interim #1	35 subjects with 12 months *45 subjects with 6 months	66%
Interim #2	*80 enrolled subjects with 12 months *35 subjects with 18 months	80%
Interim #3	*80 enrolled subjects with 18 months *35 subjects with 24 months	92%
Final	80 enrolled subjects with 24 months	100%

Using these percentages, the alpha level threshold used to determine treatment effect significance at each analysis was derived using the Lan-DeMets alpha-spending function with O'Brien-Fleming parameterization and assuming a one-sided, overall type I error rate of 2.5%. The one-sided significance thresholds are 0.0058, 0.0103, 0.0156, and 0.0190 for the first, second and third interim analyses and the final analysis, respectively, in the scenario above.

